C.7. Exercise ergometry will be conducted by a trained PROSPR exercise physiologist in accordance with the 2003 American Thoracic Society and American College of Chest Physicians guidelines (2003). We chose to use cycle ergometry instead of other modalities (e.g., a 6-minute walk test) to induce exertional dyspnea because a stationary bicycle makes it easier for us to deliver oxygen, monitor the physiologic parameters and work rate, and minimize falls. On the first day, we will administer the baseline questionnaires, including demographics, medication history, performance status, Edmonton Symptom Assessment Scale, dyspnea survey, cancer dyspnea scale, and dyspnea modified Borg scale. We will also measure patients' height, weight, resting ECG, resting blood pressure, and resting heart rate.

Before the start of exercise, research staff will explain the exercise test sequence to the participants, including how to use the dyspnea modified Borg scale. The patient will be asked to pedal at a cadence of approximately 60 rpm during the test. The metabolic cart (Parvo True One, Sandy, UT) will be used to monitor cadence, measure work rate during the exercise test, and control resistance on the cycle ergometer. Patients will begin by pedaling with no resistance for 60 seconds, followed by a warm-up stage of 120 seconds, pedaling at 10 watts (W) of resistance for the first minute and 20 W for the second minute. Their blood pressure and heart rate will be recorded every 2 minutes. Oxygen saturation and electrocardiography results will be monitored every 2 minutes during the exercise sessions. The dyspnea modified Borg Scale will also recorded every minute. Patients will perform cycle ergometry tests at an increment of 10 W/min without oxygen until they experience volitional fatigue. During the 3-minute recovery stage at 10 W, their blood pressure, heart rate, and dyspnea modified Borg scale (rating of perceived dyspnea scale, RPD) will be recorded every minute.

After at least a 2-hour rest period, patients will perform a structured exercise session, with an initial warm up period of ≤ 3 minutes followed by constant work rate cycle ergometry at 80% of the peak work rate and using LFAir, until they experience volitional fatigue. The work rate during this test will be used for stratification.

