During the second session, 3±2 days later, patients will be asked to repeat the structured exercise with one of the four study interventions. The study assessments conducted on the first day will be repeated. We will use the constant work rate test for the comparison because it has been found to be more responsive for dyspnea than have incremental tests (Teunissen et al. 2007). A gas exchange analysis will not be conducted because the high flow and oxygen content can interfere with measurements of VO2 (ml/kg/min), VO2 (L), VCO2 (L), VE (L), PetO2 (mm Hg), and PetCO2 (mm Hg), making accurate assessments infeasible. After consulting with our pulmonary collaborator and exercise physiology team (PROSPR), we have decided to measure the work rate and use this as a factor for stratification.

Although we do not expect patients to experience desaturation during exercise based on our previous studies, if we find significant hypoxemia during testing with LFAir or HFAir (and even LFOx and HFOx) arms, patients will not be able to continue with this study and will be considered as dropouts. The termination point is defined by (1)

2014-0971 Rev. 9/17/18 Page 9 of 15

participant volitional fatigue, (2) abnormal hemodynamic responses to increasing workload, (3) inability to maintain bike cadence, (4) arrhythmias detected on the ECG including changes suggesting ischemia, (5) loss of any monitoring signals, or (6) hypoxemia [O2 saturation <88%] while exercising. Patients will be monitored throughout structured exercise testing, and will have access to urgent medical care if needed. Because this study is designed to induce dyspnea with exercise and some participants had to stop the exercise testing due to leg cramps before they became dyspneic, we will ask study participants not to continue with the rest of the study if their maximum level of dyspnea Borg scale intensity is less than 4/10 by the end of the first incremental test (in keeping with inclusion criteria #2). We will enroll a total of 50 patients who completed all 3 exercise tests and had dyspnea of at least 4/10 at the end of the first incremental test.

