parameters as covariates: flow rate, oxygen, flow rate-oxygen interaction, work rate, and baseline dyspnea at rest, prior to the first exercise test. Isotime is defined as the time of the last set of measurements before completion of the baseline constant work rate test. Because of HFOx, VO2 max cannot be accurately measured. Instead, we will calculate the work rate (in watts), defined as the resistance of the flywheel x distance/revolution (m/revolution) x pedaling rate (revolution/min) x time(minute).

Because dyspnea is also repeatedly measured over time, secondary analyses will include a mixed-effects linear model on the longitudinal dyspnea scores, using the same 5 model parameters. For all analyses, we will use data graphs and residual analyses to verify assumptions, with data transformations as necessary. If more than 10% of patients are missing data, we will use multiple imputation in our analyses. Recognizing that dyspnea in cancer patients may have multiple etiologies, we will document its potential causes and perform subgroup analyses to determine whether a particular patient group benefits more from the study interventions. These analyses will be considered exploratory and hypothesis-generating. If y is the endpoint, x1 is the flow rate (1 for high and 0 for low), and x2 is oxygen (1 for oxygen and 0 for ambient air), we will fit the following linear model: y = a + b1*x1 + b2*x2 + b3*x1*x2, with some additional terms. The effect of the flow rate (i.e., the adjusted mean difference between high and low flow) can be calculated as b1 for ambient air and b1 + b3 for oxygen. Similarly, the effect of oxvgen can be calculated as b2 for low flow and b2 + b3 for high flow. Approximate 95% confidence intervals for these effect estimates can be computed given the estimated covariance matrix of the model parameters.

We will estimate the proportion of patients who complete the study; this analysis will include an appropriate 95% confidence interval.

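### The plan gives no usable rule for a second test that ends before isotime, and the longitudinal Borg model lists no explicit time term, so choices left open can materially change the estimated effect size

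*Combined protocol and SAP*

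**What the plan says.** Section D.2 analyses the Borg score at isotime with a general linear model. Its five parameters are flow, oxygen, their interaction, work rate and resting dyspnea before the first test. On timing it says: "Isotime is defined as the time of the last set of measurements before completion of the baseline constant work rate test".

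Under C.7 the baseline test is "constant work rate cycle ergometry at 80% of the peak work rate and using LFAir, until they experience volitional fatigue". For the second session, "patients will be asked to repeat the structured exercise with one of the four study interventions". The listed termination points include volitional fatigue, loss of cadence and hypoxemia, and patients with significant hypoxemia are called dropouts.

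The whole missing-data provision in D.2 is: "If more than 10% of patients are missing data, we will use multiple imputation in our analyses".

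For the repeated scores, "secondary analyses will include a mixed-effects linear model on the longitudinal dyspnea scores, using the same 5 model parameters". The displayed model equation is followed by "with some additional terms", which are not named.

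Table 2 footnote 10 and D.2 both give work rate in watts, but as a product that includes time in minutes.

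**The concern.** Isotime is fixed before randomisation, which is sound, but nothing ensures that the second test reaches it. The patients who fall short are not a random subset if they stop because dyspnea rose faster that day. Should treatment relieve dyspnea and lengthen exercise, as A.1 and A.3 hypothesise, early stops collect in the control groups and remove their worst scores. Complete cases then understate the effect. So does imputation from treatment and resting covariates alone, because those variables do not show that the early stoppers were on steeper trajectories.

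The longitudinal model has a related problem. Dyspnea rises through a test and tests differ in length, so an average over all recorded minutes mixes how breathless patients were with how long they lasted.

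D.1 says that the main purpose is preliminary effect sizes, and B.5 says that the results decide whether a larger trial follows. A materially wrong estimate would carry into that decision.

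**Working it through.** **1. The plan's own figure.** The plan states no bias figure; its nearest number is 86% power. Main effect: SE = SD x sqrt(2/20), so 1 SD gives noncentrality 1/0.316 = 3.16. Interaction: SE = SD x sqrt(4/10), so 2 SD gives 2/0.632 = 3.16. Two-sided 5% power on 34 df is 86.7% for each, which agrees with D.1. At 20 v 20, an effect attenuated to 0.65 SD would have about 52%.

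**2. What the imputation clause leaves open.** 10% of 40 is 4 and 10% of 50 is 5. Up to 4 (or 5) missing patients therefore have no stated handling. Above that, no predictors are named.

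**3. Primary analysis, illustrative.** The simulation had 40 patients (10 per arm) and 600-1000 trials per setting. Assumptions, none from the documents: resting Borg mean 1.2, stopping limit mean 7, median dyspnea-limited test 6 min, per-test log-SD 0.20, integer scores. The table gives the flow main effect. *Covariate-only* means complete cases at 10% missing or less and imputation from the model covariates above that. *Own-trajectory* means imputation from the second-test minute scores, the baseline score at the same minute, treatment-by-minute terms and the covariates.

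| Setting | No missing data | Covariate-only | Own-trajectory |
|---|---|---|---|
| 25% slower rise, all stops for dyspnea | -1.22 | -0.65 | -1.17 |
| 25% slower rise, half of stops for dyspnea | -1.05 | -0.62 | -1.02 |
| Constant 1-point relief, all stops for dyspnea | -0.95 | -0.68 | -0.93 |
| Constant 1-point relief, half of stops for dyspnea | -0.98 | -0.76 | -0.97 |
| Stopping unrelated to dyspnea and treatment | -0.92 | -0.83 | -0.91 |
| Leg-limited, no dyspnea effect, legs last 25% longer | 0.00 | +0.21 | +0.02 |
| Leg-limited, no dyspnea effect, legs last 25% shorter | 0.00 | -0.38 | -0.08 |
| Leg-limited, 15% slower rise, legs last 25% shorter | -0.56 | -0.82 | -0.61 |

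In the first row a mean of 7.7 of 40 patients lack an isotime score: 31% on low flow and 7% on high flow. Over 12 benefit settings, covariate-only handling keeps 47-78% of the no-missing-data estimate and own-trajectory imputation 92-100%. In trials with 4 or fewer missing, complete cases gave -0.49 v -0.84, -0.58 v -0.94 and -0.78 v -1.06, that is 42%, 38% and 26% smaller.

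A large-sample check on different assumptions (true effect -1.0, between-session SD 0.25 to 1.5) agreed. Complete cases and imputation from arm and resting dyspnea both gave -0.94 to -0.53. Adding serial scores gave -0.99 to -0.91. With all stops from leg fatigue that treatment did not affect, complete cases gave -1.01.

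**4. Longitudinal model, by hand.** Let Borg = r + s x t, with the test stopping at limit L. The mean over minutes 1 to D is r + s(D+1)/2. Take r = 1.2 and L = 7.
- Control: D = 6, s = 5.8/6 = 0.967, mean 1.2 + 0.967 x 3.5 = 4.58.
- Treated, slope cut by 25%: s = 0.725, D = 5.8/0.725 = 8, mean 1.2 + 0.725 x 4.5 = 4.46.
- Difference without time: 4.46 - 4.58 = -0.12.
- True average difference over minutes 1 to 6: (0.725 - 0.967) x 3.5 = -0.85.

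Simulation with work rate fixed per patient gave -0.05 v -0.76, and separately programmed runs gave -0.06 v -0.77 and -0.09 v -0.79.

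**5. The work-rate definition.** Resistance (kg) x m/revolution x revolutions/min is kg·m/min, the unit that footnote 10 converts to watts. A further multiplication by minutes gives kg·m, which is work and not a rate. Read literally, the covariate grows each minute at constant load. Entered as load x minute (assumed load mean 55 W, SD 18), it moved the base estimate to -0.54 in one run and -0.56 in another. An explicit minute term gave -0.61 and -0.62.

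**The case against.** The strongest reply is that multiple imputation is planned, and nothing stops the statistician from using the minute scores that the protocol collects. That is correct. A reader might infer that the plan as written halves the effect, but the wording does not support this: covariate-only imputation is one permitted reading and own-trajectory imputation is another. What stands is underspecification above 10% and silence at or below it.

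A reader might also infer that the imputation choice could reverse the sign. None of the settings examined shows that. Nor is the bias always toward zero. C.7 records that "some participants had to stop the exercise testing due to leg cramps before they became dyspneic", and the Borg 4/10 screen after the incremental test reduces such stops without excluding them.

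It can be said that early stoppers are already covered by the 20% attrition allowance, or excluded because "We will enroll a total of 50 patients who completed all 3 exercise tests". A.2 asks both for exercise to volitional fatigue and for all dyspnea assessments. A patient who reached fatigue before isotime can be read as meeting it or failing it, so neither clause settles the matter.

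For the longitudinal model, it is fair to object that work rate as literally defined contains time, so the near-total loss in step 4 depends on reading it as one value per patient. That stands. The literal reading conflicts with the stated unit, however, and still gives no treatment-by-time term.

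Finally, the benchmark is the score a patient would have given at isotime had the test continued. The plan does not state that target. A carried terminal score answers a different question; it ranged from 65% to 180% of the no-missing-data estimate and is not a conservative bound.

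**Conclusion.** The gap is real and should be fixed, but it does not invalidate the trial. The isotime score can be missing for reasons tied to dyspnea and treatment, and methods that all fit the text gave materially different effect sizes: -0.65 against -1.17 in the base illustration. The direction is conditional: toward zero if treatment relieves dyspnea and so prolongs exercise, in other directions if it changes leg endurance, and small (-0.83 v -0.92) if stopping is unrelated to dyspnea and treatment.

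The secondary model lists no explicit time or treatment-by-time term. With a fixed work rate its coefficient is about -0.1 against a true average of about -0.8. With the literal work-rate definition it is about -0.55, so the second part depends on which definition is meant.

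All sizes rest on assumed slopes, stopping limits and test lengths. The existence of the gap rests on the text alone.

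**What to change.** 1. **Primary.** Keep the baseline-defined isotime. State that a second test ending before it gives a missing isotime score. Whatever the percentage missing, multiply impute that score from the patient's own second-test minute Borg scores, the baseline-test score at the same minute, treatment-by-minute terms and the model covariates. Tabulate early stops by arm and recorded reason. Give complete-case and carried-terminal-score results as sensitivity analyses. State how patients stopped for hypoxemia enter the analysis, with no change to the stopping rule.
2. **Longitudinal.** Add minute and treatment-by-minute terms, with a patient random intercept and a random slope only if it fits stably. Report the adjusted difference at one minute named in advance that most tests reach.
3. **Work rate.** Reconcile D.2 and Table 2 footnote 10. Remove the time factor if a rate in watts is meant, and state that the covariate is the constant-load work rate.

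The cost is wording only; minute scores, reasons for stopping and duration are already collected. There are statistical downsides. Imputation extrapolates for early stoppers: it gave 92% of the no-missing-data estimate with a convex trajectory or noisier scores, and 109% (-0.61 v -0.56) in a setting where treatment shortened leg-limited tests. At this sample size the random-effect covariance was at or near its boundary in 12-31% of imputation-model fits and 43-72% of time-model fits, so the fallback to a random intercept should be written down. A named minute near the median test end overshoots (minute 6: -1.37 v -1.22). Minute 4 gave 91-101% of truth in the 12 benefit settings, but 119% where treatment shortened leg-limited tests.

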- **Baseline exercise sessions on day 1**—Patients will first complete an incremental exercise test to familiarize themselves with the cycle ergometer and to identify their maximal work rate. They will then complete a structured exercise session with cycle ergometry at a constant work rate of 80% peak with LFAir, which will inform us of their dyspnea response and isotime.
- Use of LFAir at baseline test—Neither LFAir nor LFOx has been found to improve dyspnea in non-hypoxemic patients. This will address the placebo effect with nasal cannula use.
- Inclusion of HFOx and HFAir arms—To our knowledge, HFOx has not been tested in non-hypoxemic cancer patients. No study has examined the therapeutic role of HFAir in any patient population.
- **Inclusion of LFOx arm**—Although LFOx was found to be ineffective compared with LFAir during the 6-minute walk test, its utility has not been tested with cycle ergometry in cancer patients.
- Stratification—To minimize the possibility that baseline dyspnea and exercise performance will affect the outcome, we will stratify patients by this baseline dyspnea modified Borg Scale score at rest (0-3/10 vs. 4-7/10; >7/10 will be excluded) and by their work rate during the first structured exercise session (≤50 W vs. >50 W). The objective of stratified randomization is to ensure a balance of the treatment groups with respect to the various combinations of predictive variables (i.e., the baseline Borg scale and work rate). This will ensure that a similar number of patients from each strata are randomly assigned to each treatment arm but will not require a similar number of patients in each strata. Thus, stratification should not affect the enrollment rate.

2014-0971 Rev. 9/17/18 Page 6 of 15

C.2. Eligibility criteria. The eligibility criteria are shown in Table 1. The rationale for including patients with obstructive and restrictive lung disease in this study is that the mechanisms of dyspnea relief (e.g., trigeminal nerve stimulation and decreased breathing effort; see Figure 1) are applicable to both types of pulmonary disorder. To ensure homogeneity in the study population and patient safety, we will exclude patients with severe obstructive airway disease (FEV1/FVC <70% post bronchodilator and forced expiratory volume in 1 second <30% predicted).

Table 1. Study Eligibility Criteria

Inclusion Criteria

- 1. Diagnosis of cancer, with evidence of primary or secondary lung involvement

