randomized for the study and the number who complete it. Patients' reasons for

declining to participate will also be captured.

Our clinic has 3 physicians who are supported by a fully staffed interdisciplinary team and who see a mean of 30 patients (8-10 new consults) per day, 5 days per week. One of the physicians is embedded in the thoracic medical oncology clinic and routinely receives referrals for dyspnea.

We will document recruitment and retention rates and reasons that patients dropout. We expect that at least 80% of patients will participate in the structured exercise sessions until they experience volitional fatigue and complete all dyspnea study assessments. Because patients have to make 2 extra visits to MD Anderson for study assessment, we will provide an honorarium of \$50 gift card/study day for a total of \$100 over 2 study days. We will also provide patients a parking voucher at each study visit as reimbursement for their parking costs (up to 2 vouchers total).

C.4. Randomization. Patient randomization will be performed using the Clinical Trial Conduct website (https://biostatistics.mdanderson.org/ClinicalTrialConduct), which is maintained by the Department of Biostatistics at MD Anderson. The trial statistician will train the respiratory therapists in the use of this website for randomizing patients. We will use a computer-generated sequence in permuted blocks to randomize patients, in a 1:1 ratio, to the two treatment interventions (high flow vs. low flow and oxygen vs. air). To minimize the possibility that baseline dyspnea and exercise performance will affect the outcome, we will stratify patients by baseline dyspnea modified Borg Scale score at rest (0-3/10 vs. 4-7/10) and by work rate during the first structured exercise session (\leq 50 W vs. >50 W).

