⁶ Validated 12-item questionnaire to assess the quality of dyspnea in cancer patients during the previous few days (Tanaka *et al.* 2000). Each item has a score between 1 and 5, for a maximum of 60.

⁷ The Baseline dyspnea index (BDI) is a validated scale used to assess dyspnea under 3 domains: 1) functional impairment, which examines the impact that dyspnea has on the ability to carry out daily activities; 2) magnitude of task, which examines the type of task that results in dyspnea; and 3) magnitude of effort, which establishes the level of effort that leads to dyspnea. BDI ranges from 0 (very severe impairment) to 4 (noimpairment) for each domain, with a total score of 0 to 12.(Mahler *et al.* 1984, Mahler and Wells 1988, Witek and Mahler2003)

⁸ The Modified Dyspnea Borg Scale-Intensity is the primary outcome measure, a 0 (no dyspnea) to 10 (worst dyspnea) ratio scale validated for rating dyspnea severity (Dorman *et al.* 2007,

Powers and Bennett 1999); this will be measured every minute during exercise testing. Modified Dyspnea Borg Scale-Unpleasantness is one of the secondary outcomes.

⁹ Heart rate, respiratory rate and blood pressure will be measured at baseline and every 2 minutes during the exercise sessions. Continuous oxygen saturation and electrocardiogram monitoring will be provided during the exercise sessions, and documented every 2 minutes during testing. During the cool down period, these will be measured every 1 minute

¹⁰ Work rate (Watts) is calculated as follows: resistance of the flywheel x distance/revolution (m/revolution) x pedaling rate (revolution/min) x time (minute). One Watt is equivalent to 6 kg·m·min⁻¹. It will be measured continuously during exercise testing. We will also document symptoms (e.g. fatigue and leg discomfort) q2min during exercise testing, as well as reasons for stopping (e.g., breathlessness, fatigue, and leg discomfort) and the duration of exercise.

¹¹ Device settings include FiO₂, oxygen flow, and temperature.

¹² Adverse effects related to supplemental oxygen use, such as dry eyes, dry nose, nasal moisture, and anxiety, will be assessed using a numeric rating scale from 0 (not at all) to 10 (worst possible) before and after the intervention.

¹³ We will assess blinding (oxygen v. air) and global impression (better/no change/worse) of patients and research staff.

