To estimate the effects of oxygen and flow rate on physiologic function (respiratory rate and oxygen saturation) and exercise capacity (work rate and exercise duration), we will use mixed-effects linear models because most of these are measured repeatedly over time. Given the limited number of patients, the results will be considered exploratory. Adverse events will be assessed using a numeric rating scale from 0 to 10 before and after intervention. Differences in these scores for each type of adverse event will be analyzed using general linear models, as described above for the primary endpoint.

2014-0971 Rev. 4/20/2017 Page 13 of 15

E. DATA CONFIDENTIALITY PROCEDURES

Health information will be protected and we will maintain the confidentiality of the data obtained from the patient's chart.

Collection of identifiers: We will collect and securely store patients' identifiers (including name and medical record number). Each patient will be assigned a study number that will be the only identifier to figure in the analytical file and personal data will not be disclosed in any form. The key linking these numbers will be retained in a securely locked file by the investigator.

Data Storage: Protection of electronic and paper records will be guaranteed. All electronic records will be stored on password-protected institution computers behind the institution firewall. Any paper records will be classified and stored in locked files inside a locked office.

Training of personnel: Only MDACC personnel trained in maintaining confidentiality, the principal investigators and co-investigators, will have access to study records.

Data sharing: Study data will not be shared with any individuals or entities without an IRB-approved protocol. The data will be kept by the principal investigator in a locked file cabinet and password protected computers.

Final disposition of study records: PHI may be maintained indefinitely, aggregated in the future, and used for future IRB-approved research studies.

F. REFERENCES

1. Ats/ers statement on respiratory muscle testing. *Am J Respir Crit Care Med* 2002;166:518-624.

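### Exercise duration is one randomized value per patient, yet the plan sends it to a mixed model and names no term for the day-1 duration it already collects

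*Combined protocol and SAP*

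**What the plan says.** Secondary Objective #2 (Section A.3) asks for preliminary effects of oxygen and flow on physiologic function and on "exercise capacity (work rate and exercise duration"). Section D.2 gives all four outcomes one method: "we will use mixed-effects linear models because most of these are measured repeatedly over time". It lists no covariates for them, and it does not say whether the first session's values enter the model or how.

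Duration is recorded once per test. Table 2, footnote 10, has staff document "as well as reasons for stopping (e.g., breathlessness, fatigue, and leg discomfort) and the duration of exercise". Table 2 marks exercise test variables for both structured tests.

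Only the second structured session carries a randomized intervention (Sections C.1 and C.7). The first is a constant-work-rate test on low-flow air at 80% of peak, run "until they experience volitional fatigue" (C.7), "which will inform us of their dyspnea response and isotime" (C.1). Day-1 duration is therefore available, and isotime for the primary endpoint is derived from that same test.

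On differences between patients, C.1 names baseline dyspnea and maximal work rate as adjusters. The dyspnea models in D.2 use work rate and resting dyspnea. Baseline duration appears in neither place.

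Section C.7 lists six termination points, one of them being "5) loss of any monitoring signals". No rule says how a duration ended in that way is analysed.

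**The concern.** The word 'most' in the D.2 rationale concedes that the reason does not cover every outcome listed, and duration is the one it plainly misses. If only the randomized session is analysed, each patient contributes one duration. A random patient effect then cannot be separated from residual error, and the mixed model reduces to an ordinary linear model. If the named adjusters are the only ones used, the patient's own duration on the same test at the same relative load is left out.

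The stake is precision. The trial exists to produce preliminary effect estimates for a larger study, and it has about 20 evaluable patients per factor level. A covariate that is already recorded can narrow the interval for duration with no new data.

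**Working it through.** **1. The plan's own power, as a reference.** D.1 gives 10 evaluable patients per arm, a 1-SD main effect, a 2-SD interaction and alpha 5%. The sidedness is not stated; two-sided reproduces the figure.

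- Main effect, 20 v 20: noncentrality 1/√(2/20) = 3.162.
- Interaction, 10 per cell: 2/√(4/10) = 3.162.
- Two-sided t with 36 df: power 86.8% for each, against the stated 86%.
- Attrition: 40/(1 − 0.2) = 50, as stated.

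This power is for the Borg endpoint. No power is stated for duration. The same layout gives an unadjusted standard error for a main effect on duration of √(2/20) = 0.316 SD.

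**2. Adding day-1 duration.** Let r be the within-arm correlation between day-1 and second-session log-duration, given whatever other covariates are in the model. The documents give no value, so r is an assumption.

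- Large-sample standard-error ratio: √(1 − r²).
- Allowance for chance imbalance in the covariate: with 40 patients in four arms there are 36 within-arm df, so multiply by √(1 + 1/(36 − 2)) = √1.0294 = 1.015.

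| r (assumed) | √(1 − r²) | × 1.015 | Fall in SE | Power for 0.5 SD | Effect detectable at 86% power |
|---|---|---|---|---|---|
| no baseline term | 1.000 | – | – | 34% | 0.99 SD |
| 0.3 | 0.954 | 0.968 | 3% to 5% | 36% | 0.94 SD |
| 0.5 | 0.866 | 0.879 | 12% to 13% | 43% | 0.86 SD |
| 0.6 | 0.800 | 0.812 | 19% to 20% | 49% | 0.79 SD |
| 0.8 | 0.600 | 0.609 | 39% to 40% | 73% | 0.59 SD |

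The last two columns use 35 df and the large-sample ratio, so they are slightly favourable. A separate simulation gave falls of about 3%, 12%, 19% and 39%, in line with the corrected column.

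Put as sample size, at r = 0.5 an analysis without baseline duration would need 40/(1 − 0.25) = 53 patients to match 40 with it.

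**3. The two-session alternative.** A mixed model that takes both sessions as outcomes with a common day-1 mean was compared with covariate adjustment (600 simulated trials, 40 patients, SD units):

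- r = 0.5: 0.266 for both, against 0.310 with no baseline.
- r = 0.7: 0.226 for both, against 0.309 with no baseline.

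The two specifications are interchangeable. The loss in step 2 arises only if day-1 duration is not used at all.

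**The case against.** The strongest reply is that D.2 is silent on baseline duration and does not exclude it. The section allows additional model terms, both sessions' durations are collected, and a two-session mixed model would recover all the precision. This stands. It means the plan cannot be said to have chosen an inefficient analysis, only to have left the choice open under a rationale that does not fit.

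A second reply is that r may be low. The load is set at 80% of each patient's own peak, so a high correlation cannot be presumed. This also stands, and it is why the range starts at 0.3, where the gain is small.

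Three stronger readings are tempting, and the documents do not support them.

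- A reader might infer that pooling the sessions would roughly halve the effect. That happens only if day 1 is coded by the gas assigned later. D.2 codes flow and oxygen by what they are, and day 1 is given on low-flow air, so both indicators are 0. With that coding and a session term, the simulated mean was 0.26 against a true 0.262.
- A reader might infer that ignoring signal-loss stops costs a definite share of precision. The answer turns on when the stops fall and on the scale. On the log scale, with an assumed 5% of tests stopped and r = 0.6, the standard error rises from 0.127 to 0.163 if stops fall uniformly over the test, but only to 0.129 if they fall late. In untransformed minutes, under uniform stops, the main result is a small bias toward zero (2.5% at 5% stops).
- A reader might take a stop rate from the expectation in C.3 that "at least 80% of patients will participate in the structured exercise sessions until they experience volitional fatigue" and complete all dyspnea assessments. That figure covers non-completion for any reason and says nothing about equipment.

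**Conclusion.** The point holds as a free improvement to an exploratory secondary analysis. The stated reason for a mixed model does not apply to exercise duration, and the plan does not say how the day-1 duration is to be used. Against a second-session model without it, including baseline duration lowers the standard error by about 3% to 40% for an assumed correlation of 0.3 to 0.8. If the investigators already intend a correctly coded two-session model, nothing is lost and only the wording needs completing.

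The missing rule for signal-loss stops is a real gap, but its size cannot be judged because the documents give no rate. The primary Borg analysis, the sample size and the stated power are unaffected.

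**What to change.** In D.2, separate exercise duration from the repeatedly measured outcomes and state its model:

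- General linear model for second-session log-duration on flow, oxygen, flow-by-oxygen interaction and day-1 constant-work-rate log-duration. The residual checks already planned cover the choice of scale.
- Or, equivalently, a mixed model on both sessions' log-durations with a session term and day 1 coded as low-flow air for every patient.

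Optionally, add a sensitivity analysis (for example a censored regression) that treats tests ended by loss of a monitoring signal as right-censored, and tabulate stop reasons by arm. Limit the censoring to signal loss. Stops for hypoxemia, arrhythmia or hemodynamic response may depend on the assigned gas, so non-informative censoring would not be a safe assumption for them.

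The cost is one degree of freedom, a few lines of text and standard code. No new data are needed. The sensitivity analysis adds a distributional assumption.
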